
BACKGROUND

COVID-19 is a viral infection caused by SARS-CoV-2, which spreads primarily via respiratory droplets during close face-to-face contact (1). Pregnant women are known to be disproportionately affected by respiratory illnesses, which are associated with increased infectious morbidity and high maternal mortality rates (2). In this scenario, many expecting mothers are unable to visit the clinician or health center, especially in developing countries; this might lead to missing out on high risk factors in due course of pregnancy (3). Remote care enables a provision of obstetric care at contingency plans, in order to minimize antenatal visits, as it limits an exposure to SARS-CoV-2 for healthy pregnant women and also for healthcare providers (4). Telemedicine can potentially mitigate potential adverse effects of reduced antenatal visits. Several studies have shown that telemedicine is an effective strategy, in which applying evolving telemedicine capabilities can improve good quality care for obstetric patients (5). A systematic review suggests that obstetrical telemonitoring has a great potential for contributing with better gestational outcomes, early detection of complications, prevention of intercurrences, and providing rapid intervention even before hospitalization (6). Some studies suggest that reduced-frequency prenatal care model, technology-enhanced, is as safe as the standard model of care for low-risk pregnant women (7). Although, there is low-grade evidence published, Brazil has an incipient regulation of telemedicine and, therefore, most prenatal care has been conducted face-to-face. Here we describe a research protocol of a study whose objective is to assess the feasibility of conducting a randomized controlled trial on the effectiveness and the cost-effectiveness of prenatal care telemedicine. The null hypothesis to be tested in this study is that

there is no difference in (cost-) effectiveness on maternal health outcomes between patients undergoing standard prenatal care compared to those receiving telemedicine for prenatal care.

METHODS/DESIGN

Unblinded, parallel group, randomized controlled trial

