equal numbers in each arm by the end of the study. Blocks of varying length will be used to reduce the predictability of the allocation sequence. In advance of participant recruitment, an independent researcher will be responsible for generating the allocation sequence using the Stata program (version 2.0). Sealed envelopes will be used to assign participants to intervention groups. Thus, the allocation sequence will be concealed from all study researchers until the interventions are assigned, unless major adverse events or unexpected inconsistencies occur in the follow-up to the study.

Interventions

All eligible women who consent to participate in the study will be randomized into either usual prenatal care (UPC) or telemedicine prenatal care (TPC). The antenatal scheduling process will be similar between groups. In the UPC all appointments (at least 9) will be in person. Participants assigned to the TPC group will perform at least 6 in person appointments and 3 online appointments through the Google Meet platform; this group will have wearable for blood pressure and fetal heart home monitoring, as needed according to the guidelines defined previously by the Obstetric Outpatient Department. Consent for teleconsultation and medical device use at home will be obtained. In situations where Google Meet or internet isn't available, the appointments will be carried out by video call. Pregnant women from both arms of the study will receive standard care from the obstetric team. Clinical management will be based on evidence-based guidelines used at MTM, which is currently being revised to include remote antenatal care and will be finalized and available before collection of data. Santa Casa Hospital will provide all necessary laboratory and imaging tests. Participants from both arms of study will be advised to

10
seek obstetric emergency in case they are feeling some discomfort or pain, have any complications or need any further evaluations.

Variables and data collection

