Data collection has four components: baseline demographic characteristics, quality of life and economics data, anxiety scores and clinical outcome data. Undergraduate medical students and Gynecology and Obstetrics residents, trained in conducting diagnostic assessments, will collect data and apply the standardized questionnaires. In order to compare participants in both arms, data on clinical risk factors and socioeconomic status will be collected during the recruitment phase, using the baseline characteristics questionnaire (Table 1).

Chart 1: Baseline characteristics questionnaire

	Variable	Description or Categories
Demographic characteristics	Distance from capital	In kilometers (km)
	Age	In years
	Skin color	White, black, asian, brown, indigenous
	Marital status	Single, married/living together, separated/divorced, widowed
	Scholarly	Elementary, high school, youth and adult education, higher education
	Occupation	Currently performed job
	Work situation	Employee with a formal contract, employee without a formal contract, civil servant, self-employed, unemployed
	Working hours per day	In hours
	Income	In Reais
	People living on this income	01, 01 to 03, 04 or more
Clinical characteristics	Children who live on this income	01, 02, 03, 04 or more
	Weight at 1st medical appointment	In kilograms (Kg)
	Height	In centimeters (cm)
	Blood pressure at 1st medical appointment	In millimeters of mercury (mmHg)
	Prior parity	Number of pregnancies, abortions, childbirth, cesarean sections, molar and ectopic pregnancies
	History of premature birth or stillbirth	Yes or no
	Comorbidities	Describe chronic diseases
	Chronic use medications	Describe medications in use

Outcome variables

Severity of anxiety among pregnant women and postpartum women will be evaluated by GAD-7 scale (Chart 2), which has been validated for assessing anxiety

in pregnant women, in a study developed by Zhong and collaborators (13). This scale had good reliability, internal and external validity; patients with scores greater than or equal to 07 required careful follow-up (13).

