Clinical outcomes will be collected to explore the clinical effectiveness of the TPC based on hospital database reviews (Chart 5).

Chart 5: Maternal-fetal outcome and puerperal aspects

Maternal-fetal outcome and puerperal aspects	
Delivery methods	Vaginal or cesarean
Gestational age at birth	preterm, term, post term
Maternal complication	Infectious, hemorrhagic, none, other
Newborn's size	Small, appropriate, large for gestational age
Need for neonatal ICU	Yes or No
Breast-feeding	Yes or No; time and reason
Need to return to obstetric emergency	Yes or No; reason
Need for medical appointments in pediatric emergency	Yes or No; reason

Outcomes

Primary outcome: Mean between-group differences in GAD-7 scores.

Secondary outcome 1: difference between means, between groups, of data related to the mother: delivery mode and obstetric complications.

Secondary outcome 2: difference between means, between groups, of data related to the baby: gestational age at birth, birth weight, APGAR, neonatal intensive care unit (ICU) admission.

Secondary outcome 3: economic analyses.

The quality of assistance will be evaluated by the Humanization Program for Prenatal and Birth (PHPN) criteria proposed by Brazil Ministry of Health (21). Adherence to the proposed care will be assessed by attending the consultations, carrying out the proposed exams and extra consultations in the Obstetric Emergency. The schedule intervention was present at Figure 2.

Figure 2: Flow Chart of recruitment, intervention and evaluations

Figure 1: Flow Chart of recruitment, intervention and evaluations								
MOMENT	Study period							
	Screening	Allocation	Post Allocation				Finalization	
-t1	0		t1	t2	t3	t4	t5	t5
RECRUITMENT								
Eligibility evaluation	X							
ICF *		X						
Allocation		X						
INTERVENTION								
SG and GC: In-person queries			X	X	X	X		
SG: Telemedicine consultations			X	X	X	X		
EVALUATION								
Sample ascription	X							
Anxiety (GAD-7)			X	X	X	X		
LQ and costs (E5-5D)			X	X	X	X		
Personal costs								
Implementation costs							X	
Clinical Outcomes							X	
Feasibility								X
Accession								X
Quality (PHN)								X
Cost-effectiveness								X

Legend

t1 Initial eligibility evaluation through referral to the PN
 T0 Allocation based on eligibility criteria
 t1 First Trimester
 t2 Second trimester
 t3 Third trimester
 t4 Puerperium

Analysis plan

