Data acquired according to this protocol will be stored in a password-protected database on a secure network. All entries will be made by an authorized member of the investigator's staff. Data will be entered into the study database and verified through the use of programmed edit checks for accuracy and completeness. The corrected data and a complete audit trail of corrections will be retained. An internal

audit of a sample of the data will be conducted quarterly to assure quality. The investigator will ensure that participants' anonymity is maintained. Participants will not be identified by their names, but by their assigned identification number and initials. Signed informed consent forms, will be maintained securely. Only authorized members of the investigator's staff will have access to the final trial dataset. All information regarding the study data or results supplied to the investigator is privileged and confidential information. The investigators agree to use this information to accomplish the study and will not use it for other purposes.

Safety management

The research team will be composed of a principal investigator, co-investigators and a trial statistician. A data monitoring committee is not required as the study management group will liaise every month to review interim analysis and monitor adherence. The principal investigator will make the final decision to terminate the trial in the event that uptake rates fall below pre-trial levels in either intervention arm. It is not anticipated that there will be premature ends of study. However, if this occurs, then the data will be analyzed and results circulated among the team members. The ethics committee will be notified of any premature termination and the reasons for termination. Adverse events or other unintended effects of trial interventions that come to the attention of trial investigators will be reported immediately to the study management Group. All protocol amendments will be submitted to the ethics committee for review and approval before implementation and to trial registries.

Trial status

This study protocol aims at disseminating and discussing a new model of prenatal care. It will be presented at the IRB of the Irmandade Santa Casa de Misericórdia de Porto Alegre and after approval the recruitment will start.

Dissemination policy

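### Maternal complication, part of secondary outcome 1, is classified from hospital records by study staff with no masking of arm and no category definitions, although partial masking would cost little

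*Combined protocol and SAP*

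**What the plan says.** The design line under METHODS/DESIGN reads "Unblinded, parallel group, randomized controlled trial", with no exception for outcome assessors or record abstractors. Under Randomisation, concealment applies only to the sequence and ends at assignment: "the allocation sequence will be concealed from all study researchers until the interventions are assigned".

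Under Variables and data collection, the collectors are named: "Undergraduate medical students and Gynecology and Obstetrics residents, trained in conducting diagnostic assessments, will collect data". Clinical outcome data are one of the four components they collect. Under Data protection and participant confidentiality, "All entries will be made by an authorized member" of the investigator's staff, supported by programmed edit checks, an audit trail and a quarterly internal audit of a sample.

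Under Outcome variables, the source is given: "Clinical outcomes will be collected to explore the clinical effectiveness of the TPC based on hospital database reviews (Chart 5"). In Chart 5, maternal complication has the options "Infectious, hemorrhagic, none, other". The row "Need to return to obstetric emergency" and the matching pediatric row are yes/no with an open reason. The Outcomes section puts obstetric complications in secondary outcome 1, beside delivery mode. Figure 2 places clinical outcomes in the finalization stage.

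**The concern.** Care cannot be blinded here, but reading a record afterwards and assigning a category is a separate step that can be masked at least in part. As written, someone who may know the arm decides whether a minor or borderline event is *none* or *other*, and no definition constrains that choice.

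The existing safeguards do not cover this. Edit checks and audits find missing, implausible or mistyped values. A defensible category chosen with the arm in mind passes all of them.

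What is at stake is the between-arm estimate for obstetric complications, which readers will use when judging whether the hybrid model loses any quality of care. The Discussion states that the new model aims at similar effectiveness, so an expectation exists that coding could follow. Which way it would push the coding is not known.

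**Working it through.** **1. Is masking provided anywhere?** The plan has no figure to reproduce on this point, so the check is of text.
- METHODS/DESIGN: unblinded, no exception.
- Randomisation: sequence concealed until assignment only.
- Variables and data collection: students and residents collect; masking not mentioned.
- Data protection: investigator's staff enter; masking not mentioned.
- Chart 5: no category definitions and no coding rule for reasons.

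There is no provision for masked abstraction, an independent assessor or adjudication.

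**2. Which rows are exposed?**
- *Maternal complication*: open to judgement and maps to secondary outcome 1.
- *Reasons for obstetric and pediatric emergency visits*: open text, but no listed outcome or analysis uses it.
- *Breast-feeding time and reason*: open text, in no listed outcome.
- *Delivery method, gestational age category, newborn size, neonatal ICU*: little discretion for an abstractor.

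**3. How much does one recoded woman move the rate?** Inputs from Sample size and power calculation: 60 women in total, so 30 per arm at 1:1, or 26 per group after losses.
- One woman: 1/30 = 3.3 points; 1/26 = 3.8 points.
- Two women: 2/30 = 6.7 points; 2/26 = 7.7 points.

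**4. How large could the bias be?** The documents give no event rates. Assume a true rate p of 10% to 30% in both arms and a fraction m of 5% to 20% miscoded in one arm only.
- Events coded *none*: bias = p × m, from 0.10 × 0.05 = 0.5 points to 0.30 × 0.20 = 6 points.
- Non-events coded *other*: bias = (1 − p) × m, from 0.70 × 0.05 = 3.5 points to 0.90 × 0.20 = 18 points.

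**5. How does that compare with sampling error?** The half-width of the 95% interval for the difference is 1.96 × √(2p(1 − p)/n). With n = 30:
- p = 10%: 1.96 × √(0.18/30) = 15 points
- p = 20%: 1.96 × √(0.32/30) = 20 points
- p = 30%: 1.96 × √(0.42/30) = 23 points

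With n = 26 and p = 20% it is 1.96 × √(0.32/26) = 22 points.

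**6. Would recoding change significance?** At 20% in both arms there are 0.20 × 30 = 6 events each. Fisher's exact test after recoding events in one arm to *none*:
- two recoded (4 v 6): p = 0.73
- five recoded (1 v 6): p = 0.10
- all six recoded (0 v 6): p = 0.02

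The largest over-coding case in step 4 gives 10% + 18% = 28%, or 0.28 × 30 = 8.4 women, against 3. Rounding up to 9 v 3 gives p = 0.10.

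**The case against.** The strongest reply is that the plan never says abstractors know the arm, and the sentence on data entry sits under a data-protection heading and does not say who classifies outcomes. That is fair. The point rests on silence together with the unblinded label. Nor do the documents say that the residents who collect data also treat trial women. But nothing in the plan, followed as written, would prevent arm-aware coding.

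A second reply is that masking would be incomplete. An abstractor must find the woman's own record, participants carry initials as well as a number, notes may mention teleconsultation, and treating staff wrote the records knowing the arm. All of this stands. It limits the gain from masking, but written definitions help even where masking fails.

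A third reply is that sampling error dominates in 60 women. It does. A reader might infer that a few coding choices would decide the safety comparison; steps 5 and 6 do not support that.

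Two other strong readings also fail. One is that the primary outcome is affected, because the METHODS/DESIGN text also names clinical effectiveness as primary. The Sample size and Outcomes sections both define the primary outcome as GAD-7, and that wording conflict is a separate matter. The other is that staff could dismiss events as unrelated to care; Chart 5 has no relatedness field.

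**Conclusion.** The point holds in narrow form. For maternal complication, which feeds secondary outcome 1, the plan leaves an avoidable route for knowledge of arm to influence classification. The visit reasons share this weakness to a lesser degree and have no listed use.

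The size is 3.3 points per recoded woman with 30 per arm, or 3.8 with 26. Under the assumed rates and miscoding fractions, total bias runs from about 0.5 to 18 points, the upper end only if a fifth of uncomplicated women in one arm are over-coded. This biases the estimate in a way its interval does not show, but would rarely change significance. GAD-7 is untouched. The event rates and miscoding fractions are assumptions, and so is the direction of any bias. The change is worth making because it is cheap, not because the trial's main conclusion depends on it.

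**What to change.** In the Chart 5 text and in the data-entry text under Data protection, state that:

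1. Maternal complication categories and visit reasons have written definitions, including what separates *none* from *other*.
2. Chart 5 is abstracted at finalization from delivery, neonatal and emergency records, by an existing team member (for example a student) who did not care for that woman and works from a list without arm.
3. Entries are locked before linkage to the allocation list.
4. The existing quarterly audit re-checks a sample under the same conditions.

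The cost is protocol wording, a short definitions sheet and assignment of about 60 records. The documents do not give staff numbers, so the sponsor should confirm that a non-treating abstractor is available. The downside is that masking stays partial, and it cannot undo how treating staff recorded events. The change adds little for delivery method, gestational age category, newborn size or neonatal ICU admission. The listed records may not hold breast-feeding duration and reason, so that row may need its own source.

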Author's contributions: Conceptualization, Methodology, Data curation, Writing-Original draft, Writing - Review & Editing: TC, AS, LC. Methodology, Data curation, Data Visualization and Analysis: AJB, BNF. Data Visualization and Analysis: SCC, CDT. All authors contributed to interpretation of the data, revision of the manuscript, and approved the final manuscript. AS is the guarantor. The corresponding author attests that all listed authors meet authorship criteria and that no other meeting the criteria has been omitted.

Acknowledgements: We are grateful to Mario Totta Maternity and Santa Casa de Misericórdia staff and resident doctors, who will support the data collection process. We also appreciate the research team members and the mothers and their babies who voluntarily participated in the study.

ABSTRACT

Background: COVID-19 pandemic and its social isolation has increased awareness of barriers to obstetric care, resulting in lower access for pregnant and postpartum women and forcing health care providers to redesign antenatal care service models. The adequacy of the Brazilian prenatal care model aims to ensure attendance, even in situations of high logistical complexity. **Methods:** This is a superiority hypothesis randomized clinical trial protocol, comparing telemedicine prenatal care to traditional prenatal care for low-risk pregnancies. This is an unstratified 1:1 allocation ratio, with a follow-up of 41 weeks (IG: 6 to 41 weeks and 06 weeks postpartum). This study also includes pregnant and postpartum women assessment of anxiety and economic evaluation of this new technology proposed. **Results:** We proposed a model of telemedicine prenatal with at least 6 in person appointments and 3 online appointments for low-risk pregnant women, based on guidelines of international and national guidelines, the study only will be start after research protocol publication and peer reviews. **Discussion:** The development of a guideline for a hybrid in-person-virtual prenatal care model aiming at reducing face to face medical appointments may lead to lower costs and decrease transmission of SARS-CoV-2 in the community, in with, activities will enable a similar effectiveness, and no reduction to the quality of care. **Trial Registration:** 48740621.9.0000.5335.

Keywords: prenatal care, COVID-19, telemedicine, health technology assessment, management guideline, randomized clinical trial.

Trial registration: 48740621.9.0000.5335. Approved at **DATA, 2023.**

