Superiority randomized controlled trial (RCT), comparing standard prenatal care and telemedicine prenatal care, with allocation ratio 1:1 and maximum follow-up 41 weeks (6 weeks pregnancy to 6 week postpartum) will be conducted. The primary outcome will be maternal anxiety and clinical effectiveness of both approaches. The SPIRIT guidelines (8) will be applied to assess the current RCT, and it is included in Appendices. A cost effectiveness study will also be conducted in the present study. The trial is registered to the International Standard Randomized Controlled Trial Number 48740621.9.0000.5335.

Setting

This study will be conducted at Santa Casa de Misericórdia of Porto Alegre - Santa Clara Hospital - Mario Totta Maternity (MTM), a teaching institution for residency and academic training in obstetrics. On average 3000 pregnant women attend prenatal care at MTM, by Brazil's Public Health System – the SUS (Unified Health System) every year, 14% of which are considered low- risk pregnancies. The MTM catchment area includes local, metropolitan and also regional population and has approximately 3000 deliveries per year.

Participants

The population of study includes every pregnant woman who seeks care in the obstetric outpatient clinics at Santa Casa antenatal care, by SUS and is classified as a low-risk pregnant. Those women who attend their first antenatal care at 6 to 12 weeks gestation at MTM using the public health system (SUS) will be screened for this study. We will classify low-risk according to the Brazilian Ministry of Health criteria, which includes patients that have no individual or social risk factors or history of previous obstetric complications, or any disease or condition that may interfere negatively in the pregnancy course (9). This criteria has been validated in several studies that had been carried out in Brazil, in which the prenatal care model is focused on well-being and safety of low-risk pregnant women (7) (10) (11).

Eligibility criteria

Inclusion criteria: Low-risk pregnant women, age between 18 to 34 years; gestational age less than 13 weeks at the first consultation and Portuguese native speaker.

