Exclusion criteria: Patients with clinical evaluation of high-risk pregnancies will be excluded, including chronic hypertension, diabetes mellitus, obesity, multiple pregnancies, severe COVID-19 infection, previous thromboembolic event, acute or chronic hematological events (eg, thrombus formation isolated to thrombophilia), use of anticoagulants, cardiovascular disease, lung disease, kidney disease, immunosuppression, severe mental disorder, recurrent abortion, previous premature birth, previous or current cancer.

Sample size and power calculation

The sample size calculation was based on the primary outcome - difference between scores on the GAD-7 anxiety scale -, compared to means, estimated at 4 points, and standard deviation of 4 points. A sample of 26 patients each group is needed to have 80% power, at the 5% significance level; considering losses of 15% in the follow-up, the final size of the intended sample will be 60 patients. Recruitment will continue until target sample size is reached. The sample was calculated using the formula for superiority randomized clinical trials proposed by WANG et al., 2017 (Figure 1):

$$n_1 = \left\lceil \frac{(z_\alpha + z_\beta)^2 (\sigma_1^2 + \sigma_0^2 r)}{(d - \delta)^2} \right\rceil,$$

$$n_0 = \left\lceil \frac{(z_\alpha + z_\beta)^2 (\sigma_1^2 / r + \sigma_0^2)}{(d - \delta)^2} \right\rceil.$$

Figure 1: formula for superiority randomized clinical trials.

Recruitment

The recruitment population includes pregnant women presenting for their first antenatal visit at 6 to 12 weeks of gestation. Participation in the study will be followed until completion of the postpartum period.

Eligible participants will receive information about study design, objectives, risks and benefits in adapted language, participant information leaflet and participant consent form (Appendices).

Randomisation

The randomization process in this RCT will use random permuted blocks to ensure similar numbers of participants in each intervention arm throughout the trial and

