This protocol follows the Standard Protocol Items for reporting: Recommendations for Intervention trials (SPIRIT) guidelines. We will inform all users and stakeholders and publish the results of the CRCT in peer-reviewed open-access journals. The final manuscript will be written based on the recommendations of the Consolidating Standards of Reporting Trials (CONSORT) guidelines for parallel and superiority trials. Results will also be presented at scientific meetings and congresses. We will report any change in the study outcomes, study design, sample sizes, or significant administrative aspects that will impact the study's design when disseminating the findings. Authorship will be in line with the recommendations of the International Committee of Medical Journal Editors. Knowledge translation tools will be carried out to disseminate the study for the population.

RESULTS

We proposed a model of telemedicine prenatal with at least 6 in person appointments and 3 online appointments for low-risk pregnant women, based on guidelines of international and national guidelines, the study only will be start after research protocol publication and peer reviews.

DISCUSSION

This study aims the development of a guideline for a hybrid in-person- virtual prenatal care model. This new model of care aiming at reducing face to face medical appointments, particularly important in COVID-19 pandemic and in distant communities, with restricted access to specialists, especially in a country of continental dimensions such as Brazil. Complemented by the economic evaluation of the proposed new technology, aims to enable a similar effectiveness, with no reduction to the quality of care and reduced costs.

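### The abstract and discussion aim at similar effectiveness with no loss of quality, but the trial is specified as superiority with no margin, so it cannot support a conclusion of similarity

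*Combined protocol and SAP*

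**What the plan says.** The Methods/Design section describes a "Superiority randomized controlled trial (RCT), comparing standard prenatal care and telemedicine prenatal care". The Abstract, the sample size section and the Dissemination policy also call it a superiority trial. The null hypothesis in the Background is that "there is no difference in (cost-) effectiveness on maternal health outcomes between patients undergoing standard prenatal care" and those receiving telemedicine. The Outcomes section gives "Primary outcome: Mean between-group differences in GAD-7 scores", and the sample size rests on a between-group difference "estimated at 4 points, and standard deviation of 4 points". The analysis plan sets 5% tests with 95% confidence intervals, in intention-to-treat and per-protocol sets.

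The stated aim points elsewhere. The Abstract says that "activities will enable a similar effectiveness, and no reduction to the quality of care". The Discussion says that the proposal "aims to enable a similar effectiveness, with no reduction to the quality of care and reduced costs", in the same paragraph that announces a guideline for hybrid care with fewer face-to-face visits.

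No section gives an equivalence or non-inferiority hypothesis, a margin, or a rule for reading a non-significant result. This is true of GAD-7, of the maternal and newborn outcomes, and of the quality-of-care assessment by the Ministry of Health criteria. The sample size formula contains a δ, but the plan gives it no value.

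**The concern.** A superiority test answers whether the arms differ. Failing to reject a null of no difference does not show that they are alike, because a small trial often fails to reject even when one arm is worse. Claims of similarity or of no reduction need a limit on how much worse is tolerable, set in advance, and an interval that excludes anything beyond it.

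If telemedicine leaves anxiety unchanged, which is what similar effectiveness implies, the planned test will usually be non-significant. A model that is moderately worse would often give the same result. With no stated limit, what counts as similar would be settled after the data are seen. The stakes are real: the Discussion itself links missed antenatal care to worse maternal and perinatal outcomes and says that evidence on visit numbers is limited.

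**Working it through.** **Inputs.** From the sample size section: difference 4 points, SD 4, 5% significance, 80% power, 26 per group, 15% losses, 60 in total. From the schedule: GAD-7 at four times (three trimesters and puerperium). Assumed, because the documents do not give them: within-woman correlation 0.3–0.8, newborn event risks of 5%, 10% and 15%, and GAD-7 margins of 2 and 3 points.

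**The plan's own figure.** With δ = 0 and a two-sided test, n per arm = 2 × (1.960 + 0.842)² × 4²/4² = 15.7, so 16 (17 by the t-test). One-sided gives 13 per arm, or 26 in total. The stated 26 per group is therefore not reproduced at 80% power; it corresponds to 95% power two-sided. For losses, 52 × 1.15 = 59.8, which matches 60, whereas 52/0.85 = 61.2 gives 62 in whole arms. This discrepancy is a separate matter. Below, 26 analysed per arm is taken as stated, with 30 per arm (no losses) beside it.

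**GAD-7 at one visit.** Half-width = t(0.975, 2n−2) × SD × √(2/n).
- n = 26: 2.009 × 4 × √(2/26) = 2.009 × 1.109 = 2.23 points
- n = 30: 2.002 × 1.033 = 2.07 points

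For a true worsening of 2 points, the noncentrality at n = 26 is 2/1.109 = 1.80. Power is 0.42, so the test is non-significant about 58% of the time. At n = 30, power is 0.48 and the figure is 52%.

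**GAD-7 averaged over four visits.** The planned mixed model or GEE could target an average. With correlation ρ, the SD of a woman's mean is 4 × √((1 + 3ρ)/4).

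| ρ (assumed) | SD of mean | Half-width, n = 26 | Non-significant if truly 2 points worse |
|---|---|---|---|
| 0.3 | 2.76 | 1.5 | 27% |
| 0.8 | 3.69 | 2.1 | 52% |

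**Newborn event.** At an assumed 10% risk in both arms, half-width = 1.96 × √(2 × 0.10 × 0.90/n) = 0.163 at n = 26 and 0.152 at n = 30, or about 16 and 15 percentage points. If neonatal ICU admission rose from an assumed 5% to 15%, the exact power of Fisher's test is 0.08 at n = 26 and 0.09 at n = 30, so the rise would be missed about 91–92% of the time.

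**What a margin would require.** For non-inferiority on GAD-7 at one visit (true difference 0, one-sided 2.5%, 80% power), n per arm = 2 × 4² × (1.960 + 0.842)²/M² = 251.2/M².
- M = 2: 62.8, so 63 per arm; 63/0.85 gives 75 per arm, 150 in total
- M = 3: 27.9, so 28 per arm; 28/0.85 gives 33 per arm, 66 in total
- Margin with 80% power at 26 per arm: √(251.2/26) = 3.1 points

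An interval of ±2.2 points cannot fit inside ±2 wherever it is centred. At one visit the planned size could therefore support only a margin of about 3 points or more, which is over three quarters of the 4-point effect the trial is sized to detect.

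**The case against.** The strongest reply is that the plan never takes the faulty step. A reader might infer that a non-significant GAD-7 result will be used to justify a guideline replacing in-person visits, but no section says so. The analysis plan commits to effect estimates with 95% confidence intervals, which would expose the uncertainty, and the Dissemination policy commits to CONSORT reporting for superiority trials. This stands, and the point is limited to what the wording leaves open.

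A reader might also infer that design and aim flatly contradict each other. That goes too far. The similarity sentences are loosely built and can be read as describing the care model rather than a trial conclusion. The objective in the Background is the feasibility of a randomized trial. Seeking lower anxiety while hoping that clinical outcomes are no worse is coherent; what is missing is a criterion for the second part.

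Nor is GAD-7 the only comparison. Methods/Design includes clinical effectiveness in the primary outcome, maternal and newborn outcomes are secondary, and the economic analysis is an estimation exercise that needs no equivalence margin. The clinical and quality comparisons, however, have no margin either.

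Finally, 58% belongs to a t-test at one visit, whereas the plan names a mixed model or GEE without fixing the visit or average to be estimated. That lowers the figure to 27–52% under the assumed correlations. It does not remove the problem, because narrower intervals still need a limit to be judged against.

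**Conclusion.** The point holds in a limited form. The Abstract and Discussion state an aim of similar effectiveness without loss of quality, and the trial as specified cannot support that as a conclusion. Intervals of roughly ±1.5 to ±2.2 GAD-7 points at 26 per arm, and about ±16 percentage points for a newborn event, leave room for differences that the plan has not declared acceptable. The GAD-7 figures rest on the plan's SD of 4 and, for the averaged version, on assumed correlations. The newborn figures rest on assumed risks. The absence of any margin or reading rule is a fact of the text and depends on none of these.

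The superiority test itself is not at fault. With a margin fixed in advance, the planned intervals could exclude large differences in anxiety, of about 3 points or more at a single visit.

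**What to change.** Keep the superiority test and the sample size, and make these changes:

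1. **Analysis plan.** State that a non-significant difference will not be interpreted as similarity, equivalence or absence of a reduction in quality.
2. **Analysis plan.** State that maternal and newborn outcomes are reported as estimates with 95% confidence intervals, and that at this sample size they cannot exclude clinically important differences.
3. **Abstract and Discussion.** Reword so that similar effectiveness and preserved quality are not conclusions this trial will support.
4. **Only if the sponsor still wants to claim similar anxiety.** Fix and justify a GAD-7 margin before recruitment, require the 95% confidence interval to lie within it, and check the sample size against that margin.

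Items 1–3 are wording only, and the Trial status section indicates that recruitment has not begun. Their cost is a more modest stated conclusion. Item 4 could need more women: under the non-inferiority assumptions above, a 2-point margin at one visit would take about 150 in total, and a rule requiring the interval to lie inside the margin on both sides would take more.
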